5.5 Adverse Reactions

Brequinar:

As discussed above, brequinar is an investigational drug that has been given to 71 patients with COVID-19. Adverse events related to brequinar were mild to moderate and infrequent, and no subjects discontinued brequinar treatment due to a related adverse event in either of the two COVID-19 studies.

Brequinar has also been given to more than 800 patients with various forms of cancer in more than 20 clinical trials and has also been tested in patients with psoriasis and those who have had a kidney or liver transplant. The most common side effects in cancer patients when given higher doses of brequinar have been:

- Thrombocytopenia, which may require replacement. Low platelet count can lead to bruising, nose bleeds, vomiting blood, bloody diarrhea, blood in the urine, bloody gums, coughing up blood, and taking longer to stop bleeding from cuts.
- Stomatitis/mucositis.
- Other risks associated with brequinar include:
 - Skin rash,
 - Nausea,
 - Vomiting,
 - Diarrhea,
 - Leukopenia,
 - Anemia,
 - Yellowing of the skin or whites of the eyes caused by high levels of the pigment bilirubin,
 - Abnormal liver tests,
 - Abnormal kidney function,
 - Cardiac complications, and
 - Fatigue

Some of these side effects were severe enough in patients treated with brequinar to require hospitalization or caused death. In most cases, these side effects went away within about 2 weeks after patients stopped taking brequinar.

Patients must be contact to study doctor/study staff if they experience any of the following:

- Discoloration/bruising of the skin or a rash of red/purple spots on your skin. These can be caused by bleeding in or under the skin,
- Nose bleed,
- Coughing up blood,

Protocol for clinical study of Brequinar

Protocol No.: 21-VIN-0372

Version No.: 2.1; Dated: 29 Dec 2021

Supersedes: 02; Date of Supersedes: 30 Sep 2021

- Blood in urine,
- Bleeding gums,
- Prolonged bleeding time from needle sticks, abrasions or lacerations,
- Vomiting blood,
- Rectal bleeding,
- Blood in stool,
- Any other unusual bleeding

Dipyridamole:

Dipyridamole will be used in this study as a pyrimidine salvage inhibitor when co-administered with brequinar (see Rationale below). When used per the labeled indications of stroke prevention and inhibitor of blood clot formation, adverse reactions at therapeutic doses are usually minimal and transient. In combination with warfarin, the dipyridamole label reports dizziness (13.6%), abdominal distress (6.1%), headache (2.3%), and rash (2.3%). Reactions from uncontrolled studies include diarrhea, flushing, and pruritus. Angina pectoris has been reported rarely and there have been rare reports of liver dysfunction. In post-marketing reporting experience, there have been rare reports of hypersensitivity reactions (such as rash, urticaria, severe bronchospasm, and angioedema), larynx edema, fatigue, malaise, myalgia, arthritis, nausea, dyspepsia, paresthesia, hepatitis, thrombocytopenia, alopecia, cholelithiasis, hypotension, palpitation, and tachycardia. In the case of real or suspected overdose, symptoms may occur such as warm feeling, flushes, sweating, restlessness, and feeling of weakness and dizziness. There is an increased risk of thrombocytopenia when taking dipyridamole. There are no clinical data to suggest that dipyridamole is beneficial for treating COVID-19.

Co-Administration of Brequinar and Dipyridamole:

This combination has not previously been tested in the clinic. There is a potential for increased bleeding when taking either drug as well as the combination, and the risk compared to brequinar or dipyridamole when administered alone is unknown. To address any potential increased risk, careful attention will be paid to laboratory reports and any increased signs or symptoms of bleeding during this study.

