Statistical methods:	
A separate, detailed statistical analysis plan (SAP) will be finalized prior to locking the database. All analyses of safety and efficacy for this study will be descriptive in nature and presented by group. Subject demographics and baseline characteristics will be summarized. Subject data listings will also be provided.
 
Summaries for quantitative variables will include the mean, median, standard error, minimum, and maximum. For qualitative variables, the summaries will include the number and percentage of subjects for each outcome, and the 95% CI, when

Protocol for clinical study of Brequinar

Protocol No.: 21-VIN-0372

Version No.: 2.1; Dated: 29 Dec 2021

Supersedes: 02; Date of Supersedes: 30 Sep 2021

	
appropriate. Any statistical testing will be considered exploratory and descriptive. All computations will be performed using SAS® (Version 9.4 or higher). Safety and tolerability will be assessed in terms of AEs, SAEs, and safety laboratory data.
 
Adverse event data will be descriptively evaluated. All AEs will be reported in data listings. The incidence of treatment-emergent adverse events, defined as TEAEs occurring after first dose will be tabulated by Medical Dictionary for Regulatory Activities (MedDRA) preferred term and system organ class, and by severity and relationship to study treatment. All laboratory results and other clinical measures will be summarized using appropriate descriptive statistics.

Ethical Issues:	
The study will commence only after a written approval is obtained from the Institutional Ethics Committee and applicable regulatory authorities. The trial will be conducted as per the biomedical research on human participants (ICMR) 2017 guidelines, New Drugs and Clinical Trial Rules (2019) of India, ICH (Step 5 'Guidance on Good Clinical Practice' ICH Guidance E6 (R2), Declaration of Helsinki (Brazil, 2013) and with procedures oriented to Good Laboratory Practice and applicable regulatory guidelines.

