15.4 Analysis of Efficacy Data

All statistical analysis will be done using SAS® Version 9.4 or higher (SAS Institute Inc., USA).

For continuous variables, the summary statistics will be the number of observations, mean, standard deviation, median, minimum and maximum values. Categorical values will be summarized using frequencies and percentages.

Primary Endpoints:

- Frequencies of grade 3 and 4 toxicities and serious adverse events (SAEs) considered by the investigator to be related to the combination, brequinar alone or placebo alone.

Because the primary study endpoint is a safety parameter no formal statistical testing will be performed for this parameter.

Protocol for clinical study of Brequinar
 Protocol No.: 21-VIN-0372
 Version No.: 2.1; Dated: 29 Dec 2021
 Supersedes: 02; Date of Supersedes: 30 Sep 2021

Secondary Endpoints:

For subjects treated with the brequinar-dipyridamole combination compared to subjects treated with the brequinar and to subjects treated with the placebo combination through Day 29, to determine:

- SARS-CoV-2 levels through Day 29 and at days 4, 8, 12, 15, 22, and 29 will be analyzed using analysis of covariance (ANCOVA) test;
- Time to symptom improvement through Day 29 will be analyzed using Kaplan-Meier time-to-event analysis;
- Percentage of subjects requiring hospital admission/re-admission as an in-patient for >24 hours through Day 29 will be analyzed using Fisher exact / chi square test;
- Percentage of subjects requiring medical attended visits, e.g., hospitalization, emergency room visits, Urgent Care/Family Doctor visits through Day 29 will be analyzed using Fisher exact / chi square test ;
- Percentage of subjects requiring supplemental support such as oxygen through Day 29 will be analyzed using Fisher exact / chi square test.

Exploratory Endpoints:

- Brequinar's pharmacokinetic profile in a subset of patients that have received brequinar as a part of therapy and have consented to provide PK samples will be analyzed descriptively.

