15.5 Safety Analysis

All safety analysis will be conducted using the safety population set.

Frequency distribution or summary statistics of all demographics variable and baseline characteristics will be generated by treatment arm.

The evaluation of the drug safety will be based on clinical AEs, vital signs, physical examination, concomitant medications and laboratory abnormalities reported during the study and incidence of adverse events and treatment emergent adverse events in each arm during the study. All safety presentations will include subjects who receive at least one dose of the study medication and will group subjects by treatment received. Frequency distributions and individual listings of all adverse events will be generated. Changes in clinical laboratory test results from baseline will be listed.

A treatment emergent adverse event is defined as any event not present prior to the initiation of the treatments or any event already present that worsens in either intensity or frequency following exposure to the treatments.

Adverse events will be coded using Medical Dictionary for Regulatory Activities (MedDRA) terms using the version that is current at the time the first subjects is enrolled and will be summarized by system organ class (SOC) and preferred term within SOC. The Common Terminology Criteria for Adverse Events CTCAE 5.0 will be used to grade the severity of adverse events.

Protocol for clinical study of Brequinar

Protocol No.: 21-VIN-0372

Version No.: 2.1; Dated: 29 Dec 2021

Supersedes: 02; Date of Supersedes: 30 Sep 2021

Adverse Events will be summarized by treatment and overall. AE summary tables will include counts of subjects and the number of events. If a subject experiences more than one episode of a particular AE, that subject will be counted only once for that event. If a subject has more than one AE that coded to the same preferred term, the subject will be counted only once for that preferred term. Similarly, if a subject has more than one AE within a SOC, the subject will be counted only once in that SOC.

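### Version 2.1 names bleeding as an unquantified risk of the combination but specifies no subject-level summary of bleeding by arm, so mild bleeding spread over several terms would be diluted and could be missed

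*Combined protocol and SAP*

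**What the plan says.** Section 5.5 (Version 2.1) states that the combination has not been given in the clinic before, that either drug or both may increase bleeding, and that "the risk compared to brequinar or dipyridamole when administered alone is unknown". Its answer is that "careful attention will be paid to laboratory reports and any increased signs or symptoms of bleeding during this study". Under brequinar, the same section lists nine named bleeding signs that patients must report, for instance "Prolonged bleeding time from needle sticks, abrasions or lacerations", and a tenth catch-all item, "Any other unusual bleeding".

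The analysis text is general:

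- **Primary endpoint (Section 15.4):** "Frequencies of grade 3 and 4 toxicities and serious adverse events (SAEs) considered by the investigator to be related", with relatedness judged for each of the three treatments. No formal test is planned.
- **AE tables (Section 15.5):** AEs "will be summarized by system organ class (SOC) and preferred term within SOC", by treatment and overall, each subject counted once per preferred term and once per organ class. Individual AE listings are added.
- **Synopsis, Statistical methods:** treatment-emergent AEs "will be tabulated by Medical Dictionary for Regulatory Activities (MedDRA) preferred term and system organ class, and by severity and relationship to study treatment". Any testing is exploratory and descriptive.
- **Section 15.1:** detailed methods and mock tables are deferred to an SAP to be finalised before database lock. The file contains no SAP text.

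**The concern.** Section 5.5 speaks of increased bleeding, which implies a comparison. The randomised contrast of combination with brequinar alone is where this trial can make it; there is no dipyridamole-alone arm. Many of the listed signs (bruising, nose bleed, bleeding gums) would often be Grade 1-2 and so fall outside the primary endpoint unless serious. In the AE tables they may be coded to different preferred terms and several organ classes.

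The primary objective is the combination's safety. If each row holds one or two subjects, a reader of the tables could conclude that bleeding was not increased when the number of subjects who bled differs clearly between arms. The data will be collected; what is missing from the protocol is the row that adds them up.

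**Working it through.** **1. Arm sizes (Sections 9.1 and 9.6).** Part 1: 4 cohorts x (8 + 4 + 4) = 64, as stated. Expansion: 32 + 16 = 48, as stated. If every cohort and the expansion fill:

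- combination 4 x 8 + 32 = 64
- brequinar 4 x 4 + 16 = 32
- placebo 4 x 4 = 16
- at the expansion dose alone: 8 + 32 = 40 v 4 + 16 = 20

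The combination-to-brequinar ratio is 2:1 in each cohort and in the expansion, so pooling these two arms does not confound arm with dose. The protocol states no power and no bleeding rate to reproduce (Section 15.2: no prospective powering).

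**2. An example that needs no assumed rates.** Suppose nine combination subjects each have a different sign and no brequinar subject has any.

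- By preferred term: nine rows of 1/64 v 0/32, each with Fisher p = 1.0.
- Grouped: 9/64 = 14.1%, Clopper-Pearson 95% CI 6.6-25.0%; 0/32 = 0%, upper limit 1 - 0.025^(1/32) = 10.9%. Fisher p = 0.027.

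Against 0/32, a single row needs 8/64 to reach p<0.05 (8/64 gives 0.049; 7/64 gives 0.091).

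**3. Dilution under assumed rates.** Let p be the risk of any bleeding sign, split evenly and independently over nine signs. A row holding k signs has risk q = 1 - (1 - p)^(k/9). The chance of two-sided Fisher p<=0.05 comes from full binomial enumeration. At p = 25% v 5%, 64 v 32:

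| Row | q, combination v brequinar | Expected subjects | Chance of p<=0.05 |
|---|---|---|---|
| Grouped (k = 9) | 25% v 5% | 16.0 v 1.6 | 70% |
| Organ class, k = 4 | 12.0% v 2.3% | 7.7 v 0.7 | 26% |
| Organ class, k = 3 | 9.1% v 1.7% | 5.9 v 0.5 | 13% |
| One sign (k = 1) | 3.1% v 0.6% | 2.0 v 0.2 | 0.08% |
| Any of nine single rows | | | 1 - (1 - 0.0008)^9 = about 0.8% |

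Organ-class rows also take in non-bleeding events such as nausea or rash. If the k = 4 row also carries unrelated events in 10% or 20% of subjects in both arms, 26% falls to about 14% or 10%.

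**4. Range over assumed rates.**

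| Any bleeding, combination v brequinar | Grouped row, 64 v 32 | Any of nine rows |
|---|---|---|
| 10% v 3% | 12% | 0.1% |
| 15% v 5% | 21% | 0.3% |
| 20% v 5% | 45% | 0.3% |
| 25% v 5% | 70% | 0.8% |
| 30% v 5% | 87% | 2.5% |

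At the expansion dose alone (40 v 20), 25% v 5% gives 46% for the grouped row.

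**The case against.** A reader might infer that AEs are tabulated only by preferred term and organ class, and that a bleeding difference cannot show. The documents support neither. The synopsis adds severity and relationship, all AEs are listed, and laboratory results, including platelet counts (Section 28), are summarised. Section 15.5 counts a subject once per organ class, so those rows pool part of the signal. Bleeding may also cluster in one or two signs. What happens is dilution.

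A reader might also take 70% against under 1% as the size of the problem. That contrast depends on assumed rates, on an even nine-way split, which is the worst case, and on pooling all doses. Section 12.9 also asks for a diagnosis to be recorded in place of its signs, so several signs could be coded as one event.

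Three further objections:

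- **The sentence in 5.5 promises monitoring, not analysis.** Monitoring is indeed provided: platelet counts, scheduled AE contacts, and a cohort safety rule that counts subjects with related toxicity of any grade (Section 12.9). But that rule mixes all toxicities and does not compare arms.
- **p<0.05 is the wrong yardstick in a descriptive trial.** This stands. The percentages above measure how visible a difference would be, and no decision is tied to them.
- **The SAP may define a bleeding group.** This also stands. That no such table will exist cannot be established; that the protocol specifies none can.

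**Conclusion.** The point holds as a gap in specification. Version 2.1 identifies bleeding as a potential risk of unknown relative size for the combination and defines no subject-level bleeding summary by arm. Under the stated tables, mild bleeding spread over several terms would be diluted and could be missed, though organ-class rows recover part of it and the listings hold the rest.

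At 25% v 5% with 64 v 32, visibility at p<0.05 is about 70% grouped, 13-26% for an organ-class row holding three or four of the signs, and under 1% over nine separate rows. The rates, the even split and the assignment of signs to organ classes are assumptions. The arm sizes assume that all cohorts and the expansion fill.

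A grouped row does not make the trial conclusive: 21% at 15% v 5%, and 12% at 10% v 3%. A null result on it would not exclude a threefold excess. It should be read as an estimate with an interval.

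**What to change.** In Section 15.5 and the SAP, pre-specify 'any bleeding event':

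- **Content:** the signs listed in Section 5.5, including the catch-all item, plus haemorrhage diagnoses recorded in place of signs under Section 12.9. A list limited to the signs would miss those.
- **Counting:** any grade, any relatedness, each subject once. Fix the term list before unblinding.
- **Reporting:** number, percentage and exact 95% CI per arm, by cohort and pooled, with the combination-minus-brequinar risk difference and its 95% CI, labelled descriptive.

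The cost is one table and a term list, with no new data and no change to patient care. The intervals will be wide, most of all within a Part 1 cohort (8 v 4), and the text beside the table should say so.

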5.6 Rationale

Rationale for the use of brequinar and dipyridamole in COVID-19 disease:

Brequinar is a potent DHODH inhibitor that blocks *de novo* pyrimidine synthesis in the host and has been previously studied in more than 1,000 cancer, psoriasis, and organ transplant patients.

Brequinar has potent *in vitro* antiviral activity against many RNA viruses including SARS-CoV-2. The *in vitro* antiviral activity of brequinar against SARS-CoV-2 is likely due to DHODH inhibition and shows nanomolar potency and a high selectivity index in inhibiting viral replication these studies. Brequinar has also been studied in two clinical trials in patients with confirmed SARS-CoV-2 infection. In these two studies, 25 were hospitalized (15 treated with brequinar) and 115 were non-hospitalized (56 treated with brequinar). Results in these 71 COVID-19 patients demonstrated that brequinar 100 mg x 5 days was safe and well-tolerated in these populations. Brequinar's antiviral activity was demonstrated in the out-patient study as shown by decreased viral load compared to placebo at days 12, 15, 22 and 29 and a shorter duration of viral shedding. The strong

Protocol for clinical study of Brequinar

Protocol No.: 21-VIN-0372

Version No.: 2.1; Dated: 29 Dec 2021

Supersedes: 02; Date of Supersedes: 30 Sep 2021

safety data in 71 COVID-19 subjects treated with daily brequinar at 100 mg for 5 days provides strong support for the further investigation of brequinar in the treatment of COVID-19.

The antiviral effects of brequinar may be blunted *in vivo* by pyrimidine salvage. One approach to enhancing the antiviral effect of brequinar is to block the pyrimidine salvage pathway by combining brequinar with a pyrimidine salvage inhibitor. Dipyridamole has been shown *in vitro* to block pyrimidine salvage and may potentiate the antiviral activities of DHODH inhibition on RNA viruses (Liu et al., 2020). Blocking pyrimidine salvage via dipyridamole shows improved *in vitro* antiviral efficacy of *de novo* pyrimidine synthesis inhibition via DHODH inhibition and will be used in this study in combination with brequinar to enhance brequinar's antiviral activity.

Dipyridamole is a well-tolerated, FDA-approved medication that is a nucleoside transport inhibitor and PDE3 inhibitor that inhibits blood clot formation and causes vasodilation. Dipyridamole was first approved by the US FDA in 1961 for prevention of thromboembolism in patients who have had cardiac valve replacement. It has also been widely prescribed in combination with aspirin to prevent stroke. There is no clinical evidence that dipyridamole used alone is effective for treating SARS-CoV-2.

The CCB-CRISIS-04 trial will study subjects who have mild to moderate COVID-19 infection confirmed by a positive SARS-CoV-2 RT-PCR qualitative test / rapid antigen test and have mild/moderate signs and/or symptoms ongoing at study entry. The purpose of this study is to determine if the antiviral activity of brequinar can be improved by combining brequinar with dipyridamole in patients infected with SARS-CoV-2.

5.7 Hypothesis

Treatment with brequinar combined with dipyridamole in patients with SARS-CoV-2 viral infection will reduce viral load, decrease time to resolution of COVID-19-related clinical signs and/or symptoms and improve clinical outcomes compared with current standard care.

6.0 STUDY OBJECTIVE

Primary Objective:

- To characterize the safety and tolerability of the brequinar-dipyridamole combination in COVID-19 subjects as measured by frequencies of grade 3 and 4 toxicities and serious adverse events (SAEs) considered by the investigator to be related to the combination.

Secondary Objectives:

For subjects treated with the brequinar-dipyridamole combination compared to subjects treated with brequinar and to subjects treated with placebo through Day 29, to determine:

- Reduction of qPCR SARS-CoV-2 levels through Day 29 and at days 4, 8, 12, 15, 22, and 29;
- Reduction in time to symptom improvement;
- Reduction in percentage of subjects requiring hospital admission/re-admission as an in-patient for >24 hours;

Protocol for clinical study of Brequinar

Protocol No.: 21-VIN-0372

Version No.: 2.1; Dated: 29 Dec 2021

Supersedes: 02; Date of Supersedes: 30 Sep 2021

- Reduction in percentage of subjects requiring medical attended visits, e.g., hospitalization, emergency room visits, Urgent Care/Family Doctor visits;
- Reduction in percentage of subjects requiring supplemental support such as oxygen.

Exploratory Objectives:

- To determine brequinar-dipyridamole combination and brequinar's pharmacokinetic profile in a subset of subjects agreeing to participate in the PK aspect of the study.

7.0 STUDY ENDPOINTS

Primary Endpoints:

- Frequencies of grade 3 and 4 toxicities and serious adverse events (SAEs) considered by the investigator to be related to the combination, brequinar alone or placebo alone.

Secondary Endpoints:

- qPCR SARS-CoV-2 levels through Day 29 and at days 4, 8, 12, 15, 22, and 29;
- Time to symptom improvement through Day 29;
- Percentage of subjects requiring hospital admission/re-admission as an in-patient for >24 hours through Day 29;
- Percentage of subjects requiring medical attended visits, e.g., hospitalization, emergency room visits, Urgent Care/Family Doctor visits through Day 29;
- Percentage of subjects requiring supplemental support such as oxygen through Day 29.

Exploratory Endpoints (PK):

- Analysis of brequinar's pharmacokinetic profile in a subset of patients that have received brequinar as a part of therapy and have consented to provide PK samples.

Clinical improvement will be defined as a 2-point or greater improvement on an 8-point WHO ordinal scale in every subject measured on each designated day, from the date of randomization through day 29. This scale has been used in the current COVID-19 outbreak.

Ordinal Scale for Clinical Improvement

Patient State	Descriptor	Score
Uninfected	No clinical or virological evidence of infection	0
Ambulatory	No limitation of activities	1
	Limitation of activities	2
Hospitalized	Hospitalized, no oxygen therapy	3

Protocol for clinical study of Brequinar

Protocol No.: 21-VIN-0372

Version No.: 2.1; Dated: 29 Dec 2021

Supersedes: 02; Date of Supersedes: 30 Sep 2021

Mild disease	Oxygen by mask or nasal prongs	4
Hospitalized	Non-invasive ventilation or high-flow oxygen	5
Severe Disease	Intubation and mechanical ventilation	6
	Ventilation + additional organ support – pressors, RRT, ECMO	7
Dead	Death	8

